Failure to start statin : Included per randomized treatment (treatment policy) Change in statin strategy : Included per randomized treatment (treatment policy) Includes discontinuation or change of statin Evidence of critical stenosis at treatment start : Included per randomized strategy (treatment strategy) Interval stent placement or bypass *: Included per randomized strategy (treatment policy strategy) Death prior to Year 2 scan : Treated as missing data (hypothetical policy)	Missing data due to missed visits or unreadable scans will be assumed missing completely at random and ignored i.e., the primary analysis will be a complete case analysis including participants with pair baseline and year 2 scans. Sensitivity analyses will include multiple imputation for missing data.
Population-level summary measure	Analysis approach
Mean change NCP volume over 2 years	Linear regression (normal errors assumption). In the event of extreme violation of normality, outcomes will be log transformed (giving a percentage change interpretation of the treatment effect). Modeling will adjust for CD4 and sex (stratification factors), and for baseline NCP volume.

\* Stented or bypassed coronary artery segments are not considered on the entry and year 2 scan as part of the read protocol for plaque volume.

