##### 3.2.1 Change NCP volume over 2 years (Primary)

- Continuous outcome:
  - Absolute change: NCP volume at 2 years – NCP volume at entry
  - Percentage change: (NCP volume at 2 years – NCP volume at entry) / NCP volume at entry (Supportive)
- Based on quantitative read whenever available (including for participants with no evidence of NCP based on the corresponding qualitative read).
  - Participants without a quantitative read and no evidence of NCP based on the corresponding qualitative read will be assigned a value of zero for both absolute and percentage change.

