## 4 Analysis Sets and Handling of Missing Data

### 4.1 Primary (Intent-to-treat)

The primary ITT sample will include all registered substudy participants who completed their REPRIEVE (A5332) entry visit. Participants registered to the substudy who failed to complete a REPRIEVE (A5332) entry visit will be considered inadvertent enrollments and excluded from all data summaries and analyses.

The primary analyses will assume all missing data are missing completely at random and be ignored. The intercurrent event of participant death during the 2 year follow-up is expected to be rare and will be handled using a hypothetical strategy – that is, outcomes unavailable due to death will be treated as missing data. Baseline and Year 2 outcomes will be described among all participants with data available at the respective time-point; analyses of change will include only participants with paired scans.

Sensitivity analyses will use multiple imputation with randomization stratification factors (sex and CD4 count) plus ASCVD risk score and BMI used to develop the model.

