## 7 Analysis Plan

### 7.1 General analysis Considerations

Outcome distributions will be described with median, Q1, Q3, P10, P90, minimum, and maximum and shown graphically. All primary treatment group comparisons will be performed ITT using a 5% type error. For continuous outcomes, inference will be based on differences in means adjusted for baseline and presented with two-sided, 95% confidence intervals.

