## Appendix I Sample Size Considerations

[Copied Verbatim from the REPRIEVE A5333S Protocol, Version 5.0, Section 9.2.]

The target sample size for the Mechanistic Substudy of REPRIEVE (A5333s) is 800 participants that will be approximately equally distributed between the study arms.

This sample size was determined to have high power to detect clinically relevant differences between the two study groups both with respect to plaque progression (among those with plaque at study entry) and rates of incident plaque (among those plaque-free at entry). Specifically, the total sample size of 800 subjects will provide 90% power to detect a 6% difference between the study groups in the percent change in NCP volume over 2 years among those with plaque at entry and 90% power to detect 13 percentage point difference in the probability of plaque development over 2 years. These effect sizes translate to a combined estimated 14 percentage point difference in the probability of NCP progression over two years and are based on the following assumptions:

50% of study participants will have evidence of NCP at study entry [Lo 2010]

A SD of 20% for the percent change over 2 years among participants with evidence of plaque at entry

An annual rate of incident plaque development of 12% among participants without plaque at entry

15% of participants entering the substudy will not be evaluable for study entry or 2 year NCP volume.

Together, the effects of statins acting in these two groups (those with and without evidence of NCP at study entry) will provide for a 7% lower prevalence of NCP after 2-years of statin treatment. Expectations for NCP prevalence and progression both as a whole and according to whether NCP was present at study entry are illustrated in the table below. These estimates are based on a simulation that further assumed the following:

Average volume NCP 250mm^3 (SD=200) among participants with NCP at entry.

Average volume NCP 40mm^3 (SD=20) at 2 years among participants without NCP at entry without statin treatment.

Average volume NCP 20mm^3 (SD=20) at 2 years among participants without NCP at entry with statin treatment.

NCP distributions were also assumed to follow a gamma distribution with size and shape parameters determine to provide the desire mean and standard deviations.

Table 9.2-1: Cells constituting the primary targeted group comparisons are shown in bold.

		At study entry			At two 2 years						

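### The SAP's multiple-imputation list omits entry NCP volume; if year-2 volumes are imputed from that list, the sensitivity analysis says almost nothing at the planned 15% missing

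*SAP*

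**What the plan says.** The primary continuous outcome is defined in SAP 3.2.1: "Absolute change: NCP volume at 2 years – NCP volume at entry". The second primary outcome, progression (SAP 3.2.2), counts any increase, or new NCP in those without it at entry.

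The analysis model is given in the estimand table in SAP 2.1: "Modeling will adjust for CD4 and sex (stratification factors), and for baseline NCP volume". The primary analysis uses participants with both scans and assumes that data are missing completely at random. The same table adds: "Sensitivity analyses will include multiple imputation for missing data".

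SAP 4.1 gives the content of that imputation: "multiple imputation with randomization stratification factors (sex and CD4 count) plus ASCVD risk score and BMI used to develop the model". Neither entry NCP volume nor randomized arm is named. The SAP does not say whether volumes or changes are imputed, or by what method.

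**The concern.** An imputation model should contain at least the variables in the analysis model, and above all the strong predictors of what is missing. Here the strongest predictor is left out.

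Table 9.2-1 (SAP Appendix I) shows the problem without simulation. In the control group, planned mean year-2 volume is 9 mm³ for those without plaque at entry and 281 mm³ for those with it. An imputation blind to entry volume draws both groups from around the overall mean of 140 mm³. Plaque-free participants then receive false growth and participants with plaque receive false regression, each of more than 100 mm³, against a planned treatment difference of 19 − 7 = 12 mm³.

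The imputation is meant to test the missing-completely-at-random assumption. Under SAP 4.2 it also decides whether further sensitivity analyses are run in the per-protocol set. A result dominated by imputation noise serves neither purpose: it can cast doubt on a real effect or hide informative missingness.

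**Working it through.** **The plan's own figure.** Appendix I states 90% power for a 6% difference in percent change, with SD 20%, 50% with plaque and 15% not evaluable. The target "is 800 participants that will be approximately equally distributed between the study arms", so 800 × 0.5 × 0.85 / 2 = 170 per arm. SE = 20 × √(2/170) = 2.17. At two-sided 5%, a 6% difference gives 79.0% power; the table's 12% − 5% = 7% gives 89.7%. The stated figure therefore reproduces for 7%, not 6%. The 13-point difference in incident plaque reproduces at 90.7%. This point does not rest on either figure.

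**How much entry volume explains.** The documents state no correlation, but the three SDs in each row of Table 9.2-1 imply it: r = (SD_entry² + SD_year2² − SD_change²) / (2 × SD_entry × SD_year2).

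- Control overall: (186² + 210² − 51²) / (2 × 186 × 210) = 0.974; R² = 0.949.
- Statin overall: (185² + 198² − 45²) / (2 × 185 × 198) = 0.975; R² = 0.950.
- Plaque at entry: control (198, 231, 68) R² = 0.924; statin (197, 216, 64) R² = 0.914.

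**Complete-case benchmark.** Residual SD given entry volume is 210 × √(1 − 0.949) = 47.5 for control and 198 × √(1 − 0.950) = 44.3 for statin, or 45.9 pooled. With 400 × 0.85 = 340 per arm, SE = 45.9 × √(2/340) = 3.5 mm³. Power for 12 mm³ is 92.6%.

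**Simulation.** 400-600 trials per setting, 400 per arm, 20 imputations, Rubin's rules, change regressed on arm and entry volume. Entry volumes are gamma with the table's means and SDs, and data are missing completely at random. The listed covariates enter as one score. Its R² with entry volume is not in the documents; it is assumed to be 0.10, with 0.40 as a range check. Sex and CD4 strata are not modelled. Rows are separate runs, so compare within a row.

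| Power when volumes are imputed | Complete case | Listed variables | List + arm | List + arm + other scan's volume |
|---|---|---|---|---|
| All, 15% of year-2 scans missing | 93.8% | 6.0% | 11.8% | 92.7% |
| All, 15% split between entry and year-2 scans | 91.8% | 14.0% | 19.5% | 92.8% |
| All, 5% missing | 93.0% | 40.3% | 48.2% | 93.2% |
| All, 25% missing | 88.5% | 2.2% | 10.0% | 88.2% |
| All, 15% missing, covariate R² 0.40 | 88.7% | 13.8% | 26.8% | 88.0% |
| Plaque at entry, 200 per arm, 15% missing | 73.7% | 8.7% | 14.3% | 72.7% |

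In the first row the SEs are 3.5, 9.4, 9.8 and 3.6 mm³. A separate simulation built from percent changes (12% vs 5%, SD 20%) and incident NCP (21% vs 8%) gave the same picture: complete case SE 3.6 and about 92%; list plus arm SE 10.0 and 13-15%; entry volume added, SE 3.6 and 92-93%.

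**If change is imputed directly** (first-row setting): 84% power on the list alone and 93% with arm.

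**Role of arm.** In the first-row setting, leaving arm out pulls the estimate toward zero, about −9.8 instead of −11.7 mm³. With arm in, it stays near the true value.

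**Limit of a simple repair.** A linear normal model with entry volume predicts, at zero entry volume, a control year-2 mean of 140 − 1.10 × 121 = 6.9 with residual SD 47.5, and a statin mean of 127 − 1.04 × 120 = 1.8 (unrounded slope) with SD 44.3. The chance of a positive draw is about 56% and 52%, averaging 54%. Planned incidence is 21% and 8%. The remaining draws, nearly half, are negative volumes.

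**The case against.** The case against is substantial.

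- **The wording is open.** SAP 4.1 says which variables are used to develop the model, not that no others may enter. Arm is also unnamed, and an analyst would probably add it. Joint or chained imputation of both volumes would bring entry volume in and remove the loss. This stands as a limit. But an analyst following the list as written could run the failing version, and adding arm alone does not repair it.
- **The outcome is change.** Imputing change directly costs little. This stands too, but SAP 4.1 does not choose that route. It also leaves participants without an entry scan lacking the baseline volume that the adjusted model needs.
- **Sensitivity analyses are read for consistency, not significance.** With arm in the model, the estimate stays near 12 mm³. True, but with SE 9.8 the 95% half-width is 1.96 × 9.8 = 19 mm³, so the interval is compatible both with no effect and with more than double the planned one.

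A reader might go further and infer three things that the documents do not support. First, that this is the only planned check on the missing-data assumption: SAP 2.1 also lists two year-2 outcomes for sensitivity analysis, defined whether or not an entry scan exists (SAP 3.2.3 and 3.2.4). They readmit participants without an entry scan, though not those without a year-2 scan. Second, that most participants lacking a year-2 scan have an entry scan: Appendix I pools the two at 15%, and Protocol Appendix II, section 8.0, makes failure to complete the entry scan a reason for discontinuation, so some may have neither. Third, that the year-2 volume outcome in SAP 3.2.4 forces volumes to be imputed: SAP 4.1 does not say that imputation applies to it.

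**Conclusion.** The point holds as a conditional one. The imputation list omits a covariate of the analysis model that explains about 95% of year-2 variance in the whole population, on planning SDs rather than observed data. If year-2 volume is imputed from the list at 15% missing, the SE rises from about 3.6 to about 10 mm³ and power falls from about 90% to about 5-15%, with or without arm. The size depends on three things: how much is missing (40-48% power remains at 5% missing), how well the listed covariates stand in for entry volume (14-27% power at an assumed R² of 0.40), and whether volumes rather than changes are imputed.

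The inference that the trial's main result is at risk would be wrong: the complete-case primary analysis is untouched. Nor is power certain to collapse, since the SAP does not fix the implementation. It should be corrected because the stated list permits a nearly uninformative analysis and a better model is available from data already collected.

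**What to change.** In SAP 4.1, state that:

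- entry and year-2 NCP volumes are imputed jointly (chained), each predicting the other, with randomized arm, sex, CD4, ASCVD risk score and BMI in the model;
- change and progression are derived after imputation;
- the method respects the zeros and skew, for example predictive mean matching or a two-part model, so that volumes are not negative and the any-increase progression outcome is not misclassified;
- total plaque volume is handled in the same way.

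If the analysis has already been run, report the imputation model actually used, and rerun it if entry volume was left out.

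The cost is slightly more analysis work. No new data are needed. It is not quite a one-variable change, because adding entry volume to a plain normal imputation would restore the precision of mean change but distort progression.

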### 4.2 Per Protocol (Treated)

All analyses will be repeated within a per protocol sample which will be limited to participants who completed 24-months study follow-up on randomized treatment.

Unless the primary sensitivity analyses demonstrate a concern for informative missingness, per protocol analyses will be limited to participants with paired entry and year 2 scans available with no additional sensitivity analyses performed. Cardiovascular risk factors associated with dropping out of the per protocol analysis will be examined.

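### The trigger in SAP 4.2 rests on an unshifted multiple imputation, so it can miss scan loss that depends on the unseen year-2 plaque outcome beyond the four imputation covariates

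*SAP*

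**What the plan says.** The primary analysis uses complete cases. SAP 4.1 states: "The primary analyses will assume all missing data are missing completely at random and be ignored". Deaths are handled in the same way: "outcomes unavailable due to death will be treated as missing data".

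The estimand table in SAP 2.1 names one kind of missing-data sensitivity analysis: "Sensitivity analyses will include multiple imputation for missing data". SAP 4.1 gives its content: "Sensitivity analyses will use multiple imputation with randomization stratification factors (sex and CD4 count) plus ASCVD risk score and BMI used to develop the model". Treatment arm and baseline NCP volume are not on that list. No shift to the imputed values, tipping-point analysis or reference-based analysis appears anywhere in the SAP.

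The per-protocol sample in SAP 4.2 is "limited to participants who completed 24-months study follow-up on randomized treatment". Its missing-data handling depends on the result of the intent-to-treat sensitivity analysis: "Unless the primary sensitivity analyses demonstrate a concern for informative missingness, per protocol analyses will be limited to participants with paired entry" and year-2 scans, with nothing further done. The SAP does not say what would count as a concern. One check in the same section is unconditional: "Cardiovascular risk factors associated with dropping out of the per protocol analysis will be examined".

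**The concern.** The SAP does not use the term missing at random, but imputing from observed covariates with no shift makes that assumption. Within levels of the covariates, missing participants are filled in as if they resembled those observed. The trigger asks this analysis whether missingness is informative. It can answer for loss that tracks sex, CD4, ASCVD score or BMI. It cannot answer for loss that tracks the unseen plaque change itself, except so far as those four variables predict plaque change.

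The unconditional look at dropout risk factors also uses observed data only. If complete-case and imputed results agree, SAP 4.2 leads the team to do no more, and a reader may take the agreement as support for the primary complete-case estimate. It does not give that support.

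**Working it through.** The plan states no figure for this point, so there is none to reproduce. The check is of the rule's logic.

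**Inputs from the documents.** SAP Appendix I: 800 participants in two roughly equal arms; 15% not evaluable; overall change in NCP volume 19 (SD 51) mm3 on control and 7 (SD 45) on statin, a difference of -12.

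**Assumptions not in the documents.** SD of change 47 mm3. Log-odds of loss 0.5 or 1.0 per within-arm SD of the outcome. All 15% of the loss follows this mechanism. Arm is in the imputation model. The standard error is then 47 x sqrt(2/340) = 3.6 mm3, with 340 = 400 x 0.85 per arm.

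**Step 1: why the two methods agree.** Let p be the share missing and let the covariates not predict the outcome. Imputed values in each arm then centre on that arm's observed mean, so the imputed arm mean is (1 - p) x observed + p x observed = observed. The two estimates coincide whatever drives the loss.

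**Step 2: size of the bias.** With 15% missing, the observed mean in an arm moves by 0.0726 SD (log-odds 0.5) or 0.1326 SD (log-odds 1.0).

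- Placebo loses high values and statin loses low values: -12 + 2 x 47 x 0.0726 = -5.2, and -12 + 2 x 47 x 0.1326 = +0.5.
- Directions reversed: -12 - 6.8 = -18.8, and -12 - 12.5 = -24.5.
- Same mechanism in both arms: -12.0 if loss depends on the within-arm outcome. If it depends on the outcome on a common scale, about -11.6 and -10.9.

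**Step 3: when covariates predict the outcome** (large-sample, first direction).

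| Covariate R2 | Log-odds | Complete case | Imputed | Gap | Bias left |
|---|---|---|---|---|---|
| 0 | 0.5 | -5.2 | -5.2 | 0.0 | 6.8 |
| 0 | 1.0 | +0.5 | +0.5 | 0.0 | 12.5 |
| 0.25 | 0.5 | -5.1 | -6.8 | 1.7 | 5.2 |
| 0.25 | 1.0 | +0.4 | -2.5 | 2.9 | 9.5 |

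At R2 = 0.25 the gaps are 1.7/3.6 = 0.5 SE and 2.9/3.6 = 0.8 SE, so the comparison does respond. About three quarters of the bias stays.

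**Step 4: a second outcome.** Simulation of percent change among those with plaque at entry (12% vs 5%, SD 20%, 200 per arm, about 15% missing, log-odds 1.0 in opposite directions by arm, 1,500 trials per scenario; true difference -7 points, SE about 2.1 to 2.2):

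- Loss driven by the unseen outcome: complete case and imputed -12.2 and -12.2 (R2 = 0), -12.2 and -12.0 (R2 = 0.05), -12.2 and -11.0 (R2 = 0.25).
- Loss driven by ASCVD score: -8.2 and -7.1 (R2 = 0.05), -9.6 and -7.0 (R2 = 0.25). Here the comparison works and imputation removes the bias.

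**Step 5: the opposite fault.** If arm is left out of the imputation model, imputed values in both arms centre on the same mean. The effect then shrinks by about p even when loss is harmless: 0.15 x 7 = 1.05 points (simulated 1.05), or 0.15 x 12 = 1.8 mm3, about 0.5 SE. The rule could then signal a concern where there is none.

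**The case against.** The strongest reply is that the SAP's reference point is missing completely at random, and that against it the comparison is informative. Step 4 bears this out for loss related to ASCVD score, and Step 3 shows a partial response even to outcome-driven loss when the covariates predict outcome. A reader might infer that the trigger cannot respond to informative loss at all. The documents do not support that.

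Several other points stand:

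- **Direction.** Large bias needs loss in opposite directions by arm, in a double-blind trial. A shared mechanism leaves the estimate near -12. No document establishes the opposite-direction pattern for plaque change. The nearest support is the crossover simulation in Protocol 9.4.1, which assumed the highest crossover among higher-risk placebo and lowest-risk statin participants. That concerns cardiovascular risk, not plaque.
- **Amount.** The 15% covers scans not evaluable at entry or at year 2, and entry loss can hardly depend on later change. Many reasons listed in SAP 5.3 (image quality, technical failure, contrast allergy) are not plaque mechanisms. If only 7.5% were outcome-driven, the opposite-direction biases would be about 3.5 and 6.5 mm3 instead of 6.8 and 12.5.
- **Model.** The illustration omits baseline NCP volume, which the planned regression includes, and uses one normal error for everyone.
- **Scope.** The trigger governs only extra per-protocol analyses. The intent-to-treat imputation, the dropout risk-factor review, the tables of discontinuation and scan availability by arm, and the characteristics of those with paired scans are all unconditional.

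These points limit the size and reach of the concern. None lets the comparison detect loss that depends on the unseen outcome beyond the four covariates.

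**Conclusion.** The concern holds in limited form. The SAP 4.2 trigger has no stated criterion. It relies on an analysis that reveals loss explained by sex, CD4, ASCVD score and BMI, and that is blind or nearly blind to loss depending on the year-2 plaque outcome beyond them. No planned analysis varies that assumption, so agreement between complete-case and imputed results should not be read as reassurance.

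The sizes above are illustrations under assumed loss mechanisms, not predictions. The bias can run in either direction or be close to nil, and it scales roughly with the share of outcome-driven loss. A reader might take the change from -12 to about zero as the expected error, or conclude that the rule suppresses a primary analysis. Neither follows: the first needs an assumed opposite-direction mechanism at log-odds 1.0, and the second misstates what the trigger controls. This is a low-cost improvement to the sensitivity analyses, not a flaw in the primary analysis itself.

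**What to change.** In SAP 4.1:

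- Name treatment arm and baseline NCP volume as variables in the imputation model, alongside the four already listed.
- Add a delta-adjusted version: shift the imputed year-2 NCP change by arm-specific amounts over a pre-specified range, and report the shift at which the primary conclusion changes. State the scale of the shift, because SAP 2.1 allows a log transformation.

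For scale, the estimate moves by p x (statin shift - placebo shift). The 6.8 mm3 scenario corresponds to shifts of about 0.48 SD per arm in opposite directions (0.15 x 2 x 0.485 x 47 = 6.8), and the 12.5 mm3 scenario to about 0.88 SD per arm. The documents fix no range, so the team must choose one and justify it clinically.

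In SAP 4.2, either make the trigger that the primary conclusion changes within that range, or run the same analysis on the per-protocol set unconditionally, which is simpler. It addresses missing scans within that set, not selection into it by completing treatment.

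The cost is SAP wording, advance agreement on the shift range, and a few reruns of an imputation already planned. No new data are needed.
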